# 9.2 Exclusion Criteria

# MAST-PROPHYLAXIS:

The presence of any of the following will preclude patient inclusion:

- Post-traumatic seizures
- Unsurvivable injury
- Previous history of epilepsy
- Patients who are taking an AED pre-TBI
- Pregnancy or breastfeeding
- Any known hypersensitivity to study drugs (or hydantoins or pyrrolidone derivatives) or any of its excipients
- Time interval from the time of admission to NSU to randomisation exceeds 48 hours

# MAST-DURATION:

The presence of any of the following will preclude patient inclusion:

- Unsurvivable injury
- Previous history of epilepsy
- Patients who are taking an AED pre-TBI
- Patient who has been clinically prescribed an AED to treat PTS (other than phenytoin or levetiracetam since current admission
- Any known hypersensitivity to study drug selected or any of its excipients
- For phenytoin: known hypersensitivity to other hydantoins
- For levetiracetam: known hypersensitivity to other pyrrolidone derivatives

# 9.3 Treatment Assignment

## MAST-PROPHYLAXIS

Patients who fulfil the eligibility criteria will be randomly assigned to either phenytoin, levetiracetam or no AED for a period of 7 days. The distribution between trial populations will be 1:1:1 (phenytoin : levetiracetam : no AED).

## MAST-DURATION

Patients who fulfil the eligibility criteria will be randomly assigned to a maximum of 3 months OR a minumum of 6 months duration of a clinically prescribed AED (phenytoin or levetiracetam, choice of drug at clinician's/site's local option). The distribution between trial populations will be 1:1 (<3 months:>6months). In the event of a seizure occurring within the trial period, treatment will continue as per local clinical guidelines regardless of the treatment arm. If treatment management changes within the trial period, patients will remain in the trial.

A secure electronic system will be used for the randomisation of suitable patients. Suitably trained staff will access the secure site and enter the patient details. 24-hour telephone support will be provided for randomisation and eligibility criteria by Trial Investigators or suitable trained delegated persons. Allocation will be stratified by depressed skull fracture (yes / no), intradural lesion (yes / no) and initial severity of injury (GCS 3-8, GCS 9-15).

# 9.4 Participant Withdrawal Criteria

Primary reasons for withdrawal may include:

- SUSAR
- Withdrawal from treatment participants may voluntarily withdraw from treatment for any reason at any time, but continue to provide follow-up data
- Withdrawal from trial participants may voluntarily withdraw from treatment for any reason at any time, and also withdraw from data collection
- Patients will be withdrawn at any time if the investigator concludes that it would be in the patient's best interest for any reason

Each patient has the right to discontinue their participation in the trial at any time. If an unconscious patient regains capacity and makes a request to be withdrawn from the trial, then this will be accepted. Incapacitated patients may also be withdrawn from the trial if the consultee requests withdrawal. In addition, the investigator may withdraw the patient from their allocated treatment arm if, subsequent to randomisation, a clinical reason for not providing the drug treatment is discovered.

## Prophylaxis

If a participant stops taking the trial drug due to intolerance, they will not be able to cross over to the other arm. In this instance the participant will be treated clinically as necessary (i.e. receive another AED or no treatment as necessary) and will be withdrawn from trial treatment However, the participant will remain in the trial and continue to be followed, unless consent to continue data collection has been withdrawn.

# Duration

If a participant stops taking the trial drug due to intolerance, they will be able to receive the other trial-permitted AED if the treating clinical team agrees. If the treating clinical team wishes to prescribe an AED other than levetiracetam or phenytoin, the participant will be withdrawn from trial treatment. However, the participant will remain in the trial and continue to be followed, unless consent to continue data collection has been withdrawn

As the trial is on an intention to treat basis, any data collected will remain in the trial and the patient will continue to be followed up unless consent to continue data collection has been withdrawn. Initially patients who have been withdrawn from the trial will not be replaced as the power calculation for the trial allows for a 12% loss to follow up, however the withdrawal rate will be monitored and patient replacement will be at the discretion of the Trial Steering Committee should it exceed 12%.

All discontinuations and withdrawals will be documented in the CRF. If a patient wishes to discontinue, anonymised data collected up until that point will be included in the analysis.

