# Stop:

Less than 30% recruitment achieved. The decision to progress will be made by the Trial Steering Committee in association with the HTA secretariat.

If the loss to follow-up (for those who have observed 6 months follow-up) exceeds 20%, without an identifiable and correctable reason it would not be feasible to progress to the substantive phase without substantial changes to the study design.

If either the DURATION or PROPHYLAXIS trial fails to recruit to target and subsequently doesn't proceed to stage 2, then recruitment to the other trial will continue under this protocol as appropriate.

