## 16 Statistics

### 16.1 Statistical methods

The main statistical analysis will be performed on an intention-to-treat basis, which will include all randomly assigned participants.

The primary endpoint (occurrence of PTS) is binary (yes / no). The primary analysis will estimate the absolute difference between the active treatment groups and control in terms of the incidence of PTS using logistic regression with an additive link, adjusting for baseline covariates (subdural haematoma (yes / no), number of lobes with a contusion (none / one / two / more than two), craniotomy or craniectomy (yes / no), depressed skull fracture (yes / no), initial severity of injury GCS 3-8 / 9-15, intradural lesion (yes / no) and will furnish the estimates with 95% confidence intervals. MAST DURATION will use a standard 2-sided p-value compared to a 5% significance level; MAST-PROPHYLAXIS will adjust for multiple testing using Dunnett's test at an overall 5% significance level stipulating that the smaller of the 2-sided p-values must be less than 2.7% to achieve statistical significance. A direct comparison between active arms (phenytoin vs levetiracetam) in MAST-PROPHYLAXIS will be a secondary analysis. The baseline covariates will be those used to stratify the randomisation: depressed skull fracture (yes / no), intradural lesion (yes / no) and initial severity of injury (GCS 3-8, GCS 9-15). Site will be handled as a random effect as there are anticipated to be 29 sites.

Sensitivity analyses will be performed to assess the influence of missing data and deviations from the intention-to-treat principle.

The GOSE will be analysed with an ordinal method adjusting for baseline covariates. Further secondary endpoints will be summarized using appropriate techniques according to whether the variable is binary, categorical, continuous or time-to-event. Categorical and binary variables will be summarized using bar charts, frequency tables and comparisons made using logistic regression.

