#### 16.3 Number of Participants to be enrolled

A 12% drop-out rate is assumed in both trials.

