#### MAST DURATION

A course of phenytoin or levetiracetam (up to 3 months) for patients with PTS in the acute phase. Hence, we are starting from the premise that the shorter AED duration is 'standard' practice. The longer AED duration course will potentially decrease the PTS rate. Therefore, the proposed study will be a superiority trial. In view of the potential for increase in side effects with a longer course, we will aim for a relatively large treatment effect of 13% (NNT 7.7), as this is felt necessary in order to lead to a change in clinical practice in the 'real -world'.

Recruiting 428 patients overall will provide 188 observations per arm. Assuming seizure rates of 12% and 25% in the intervention and control arm will provide 90% power. The expected average annual recruitment is 5-10 patients / site. We will aim to roll out the trial in 29 adult trauma-receiving hospitals in the UK. According to the timeline presented below, the recruitment will be completed in 3 years.

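### The 12% replacement trigger in section 9.4 counts withdrawals, but the 12% allowance in the power calculation is for lost outcomes, so non-responders use it up uncounted

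*Protocol*

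**What the plan says.** - **Sample size (16.3).** "A 12% drop-out rate is assumed in both trials". For MAST-DURATION, "Recruiting 428 patients overall will provide 188 observations per arm" and "Assuming seizure rates of 12% and 25% in the intervention and control arm will provide 90% power".
- **Replacement (9.4, under Duration).** Patients withdrawn from the trial are not replaced initially, because "the power calculation for the trial allows for a 12% loss to follow up". The safeguard follows in the same sentence: "the withdrawal rate will be monitored and patient replacement will be at the discretion of the Trial Steering Committee should it exceed 12" per cent.
- **Withdrawal (9.4).** Withdrawal from treatment, after which follow-up continues, is listed separately from withdrawal from the trial, which also ends data collection.
- **Loss to follow-up (11.7).** A participant who has not responded within 8 weeks of an assessment point counts as lost to that follow-up. No withdrawal is involved.
- **Pilot progression (8.3).** "If the loss to follow-up (for those who have observed 6 months follow-up) exceeds 20%, without an identifiable and correctable reason", progression is not considered feasible without substantial design changes. The same rule is written for both trials.
- **Primary endpoints (8.6.1).** Seizure within 2 weeks for MAST-PROPHYLAXIS; late seizure within 24 months for MAST-DURATION.

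**The concern.** Section 9.4 justifies its rule with one quantity and measures another. The 12% in the power calculation is the share of participants without an observed primary outcome. The monitored rate counts only people who withdraw. In a trial followed up by post, email and telephone for 24 months, silent non-response is an obvious route to a missing outcome, and it lies outside the monitored rate.

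No other numerical rule covers the gap. The only other limit on loss is applied at 6 months, for progression from the pilot, and its level is above the 12% assumed for the whole trial. In MAST-DURATION a further 18 months remain before the primary time point. The Trial Steering Committee could therefore see a withdrawal rate within 12% and take no action on replacement while the number of observed outcomes falls below the 188 per arm that the design needs.

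**Working it through.** **Inputs.** MAST-DURATION: 428 recruited, 1:1 allocation (9.3); seizure rates 25% and 12% (16.3); two-sided 5% level (16.1); 12% drop-out (16.3).

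**1. Reproduce the stated design.**
- Observed per arm: 428 × (1 − 0.12) / 2 = 188.3, against 188 stated. In reverse, 376 / 0.88 = 427.3, rounded up to 428.
- Power for two proportions, with pooled variance under the null and no continuity correction: Φ{[0.13√n − 1.96√(2 × 0.185 × 0.815)] / √(0.25 × 0.75 + 0.12 × 0.88)}, where 0.185 is the mean of the two rates.
- At n = 188: (1.782 − 1.076) / 0.541 = 1.304, so power is 90.4%. The stated 90% is reproduced.
- The MAST-PROPHYLAXIS figure also rests on observed outcomes: 1221 × 0.88 / 3 = 358.2, against 358 stated.

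In both trials the 12% is therefore the share of participants with no observed outcome.

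**2. Compare what is allowed with what is counted.**

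| Participant | Outcome lost? | Counted as withdrawn from the trial? |
|---|---|---|
| Leaves data collection | Yes, unless a qualifying seizure is already recorded | Yes |
| Stops responding (11.7) | Yes, at the follow-ups missed, unless already recorded | No |
| Stops trial treatment, stays in follow-up | No | No, reading 9.4 in context |

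The second row is the gap. If withdrawals stand at exactly 12%, the trigger has not been exceeded, and any non-response at all takes the loss beyond the allowance. At the other extreme, 20% non-response at 24 months with no withdrawals would show as a withdrawal rate of zero.

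**3. Size.** Power for MAST-DURATION with 428 recruited, by final loss at 24 months (same formula; the version with unpooled variance in brackets):

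| Final loss | Observed per arm | Power |
|---|---|---|
| 12% (plan) | 188.3 | 90.4% (90.9%) |
| 15% | 181.9 | 89.4% (90.0%) |
| 20% | 171.2 | 87.6% (88.1%) |
| 30% | 149.8 | 82.9% (83.6%) |
| 40% | 128.4 | 76.8% (77.7%) |

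Ninety per cent power needs 186 per arm, so it holds up to 1 − 372/428 = 13.1% loss. Eighty per cent needs 139 per arm, so it holds up to 1 − 278/428 = 35.0% loss. Every loss above 12% in this table is an assumption.

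**4. When 24-month loss becomes visible.** Section 8.3 plans about 50 MAST-DURATION patients in the first 12 months and 378 over the next 24. When recruitment ends at month 36, only those recruited by month 12, about 50, can have reached 24 months. A measure confined to the 24-month visit would come too late to steer replacement, so the earlier visits have to be used as well.

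**The case against.** **The 20% limit is not a rival allowance.** A reader might infer that the protocol sets its tolerated loss at three conflicting levels. It does not. There are two numbers, and 16.3 and 9.4 agree on 12%. The 20% is a pilot stop, written for both trials, and a stop line above the planning value is normal. It conflicts with nothing; it simply does not protect the 24-month allowance.

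**Loss at 6 months need not accumulate.** It is tempting to compound a 6-month loss over four periods and project very low power. Section 11.7 makes loss specific to each follow-up, so someone missed at 6 months may answer later. A late seizure recorded before loss already settles the endpoint. Seizures also reach the trial through participants' reports to the coordinating team and GP confirmation forms (8.5, 17.2). The documents support no such projection.

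**The trigger is unlikely to fire wrongly.** One could read the withdrawal rate as including people who only stop treatment. But the sentence concerns patients withdrawn from the trial, and 9.4 keeps the two kinds of withdrawal apart. The weakness is under-counting.

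**Other checks exist.** Section 16.2 allows an interim analysis to confirm the sample size, and 14 and 16.4 provide for regular committee review. It would be wrong to say that nothing could detect the problem. However, the interim analysis is optional, comes shortly before recruitment is due to stop, and has no loss threshold in the protocol. Section 16.4 sets no defined criteria for stopping.

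What stands after all this is the mismatch in 9.4, which none of these arguments removes.

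**Conclusion.** The point holds as a mismatch of measures. Section 9.4 relies on an allowance for loss to follow-up and polices it with a withdrawal rate that omits non-responders. In MAST-DURATION no numerical limit covers loss at 24 months, and the 6-month pilot rule does not supply one.

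The consequence is moderate. A final loss equal to the 20% pilot limit would leave about 88% power, under 3 points below the reproduced 90.4%. A loss of 30% would leave about 83%, and power stays above 80% until about 35% is lost. These figures assume the planned rates of 12% and 25%, equal loss in both arms, full recruitment of 428, and no outcome information from lost participants. A reader might infer that the trial could pass every check and still be badly underpowered; the documents neither predict losses of that size nor leave retention wholly unreviewed. The change is still worth making, because the rule as written measures the wrong quantity and is cheap to correct.

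**What to change.** 1. **Section 9.4.** Replace the withdrawal rate with the proportion of participants whose seizure outcome is missing for any reason (withdrawal from data collection or non-response) at the latest follow-up due. Report it at 6, 12, 18 and 24 months for MAST-DURATION and at 14 days for MAST-PROPHYLAXIS, and compare it with 12%. Do not count as missing those withdrawn from treatment only, or those whose primary outcome is already known.
2. **Section 8.3.** State that the 20% limit at 6 months is a feasibility stop for the pilot and is not the loss that the 90% power allows.

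No extra early-warning percentage at 6 months is proposed. With about 50 pilot patients recruited evenly over 12 months, only about 25 would have 6 months of follow-up when the pilot ends, too few for a tight threshold to be informative.

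**Cost.** A change of protocol wording and one more line in the monitoring report. The trigger may reach the Trial Steering Committee sooner than it would now. Replacement stays at the committee's discretion.

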# 10 Trial Treatments

## 10.1 Treatment Summary

The IMPs in this trial are levetiracetam and phenytoin. This trial has been accepted as Type A against the competent authority risk-adaption criteria, i.e. 'no higher than the risk of standard medical care'

# 10.1.1 Levetiracetam

Levetiracetam is an anti-epileptic drug widely used in clinical practice both for the treatment and prevention of post-traumatic and epileptic seizures.

## 10.1.1.1 Legal status

Levetiracetam is licensed for the treatment of epileptic seizures in adults but not for prophylaxis. It is, however, widely used off-license for treatment and prevention of PTS as discussed throughout this protocol. Standard clinical dosing as per the BNF will be adhered to.

Levetiracetam is not licensed for the treatment of PTS in children under the age of 12, although is routinely given in practice. As monotherapy, levetiracetam is only licensed from 16 years old. As an adjunct treatment however, it is licensed from 1 month of age. For children up to the age of 17 it is prescribed per body weight, in 2 categories of 'up to 50kg' and 'above 50kg'. The dosing will adhere to the children's BNF dosing regimen

# 10.1.1.2 Supply

Any product with a UK marketing authorisation may be used within the study. The IMP is to be supplied from standard hospital stock during in-patient stay and discharge prescription as appropriate. Post-discharge supplies may be supplied via primary or secondary supply routes (e.g. GP prescription supplied via community pharmacy). Any prescription charges incurred by patients or postage charges incurred by sites will be reimbursed by the trial. No trial specific labelling is required.

# 10.1.1.3 Storage conditions

Storage will be as detailed in the SmPC for specific brands and formulations in use at participating site.

## 10.1.1.4 . Maximum duration of treatment of a participant

MAST-PROPHYLAXIS: Participants will receive a course of 7 days of either phenytoin or levetiracetam or no drug.

MAST-DURATION: Participants will receive a maximum of up to 3 months or a minimum of 6 months as determined by the randomisation. The maximum possible duration of treatment during the trial is 24 months dependent on clinical need

# 10.1.1.5 Dose

1. Prescribing should be in line with the BNF recommendations and local prescribing practices. The prescription for individual patients will be left to the discretion of the prescribing clinician at the time, which should be in line with the BNF guidance but we are aware differing clinical scenarios will arise meaning individual doses may vary. Additional guidance can be found in the MAST Trial Procedures Manual.

2. If patients are experiencing recurrent seizures then the withdrawal regime should not be started and that patient should continue with their prescribed medication, as per clinical practice.

## 10.1.1.6 Administration

Levetiracetam can be administered orally, intravenously or via an enteral feeding tube

## 10.1.1.7 Known drug reactions

Drug reactions are as detailed in the SmPC.

# 10.1.2 Phenytoin

Phenytoin is an AED widely used in clinical practice both for the treatment and prevention of seizures.

## 10.1.2.1 Legal status

Phenytoin is licensed for use in the UK both to prevent and to treat post traumatic seizures following severe head injury.

#### 10.1.2.2 Supply

Any product with a UK marketing authorisation may be used within the study. Both phenytoin and phenytoin sodium products are permitted. The IMP is to be supplied from standard hospital stock during in-patient stay and discharge prescription as appropriate. Post-discharge supplies may be supplied via primary or secondary supply routes (e.g. GP prescription supplied via community pharmacy). Any prescription charges incurred by patients or postage charges incurred by sites will be reimbursed by the trial. No trial specific labelling is required.

#### 10.1.2.3 Storage conditions

Storage will be as detailed in the SmPC for specific brands and formulations in use at participating site.

#### 10.1.2.4 Maximum duration of treatment of a participant

MAST-PROPHYLAXIS: Participants will receive a course of 7 days of either phenytoin or levetiracetam or no drug.

MAST-DURATION: Participants will receive a maximum of up to 3 months or a minimum of 6 months as determined by the randomisation. The maximum possible duration of treatment during the trial is 24 months dependent on clinical need.

## 10.1.2.5 Dose

1. Prescribing should be in line with the BNF recommendations and local prescribing processes. The prescription for individual patients will be left to the discretion of the prescribing clinician at the time, which should be in line with the BNF guidance but we are aware differing clinical scenarios will arise meaning individual doses may vary. Additional guidance can be found in the MAST Trial Procedures Manual.

2. If patients are experiencing recurrent seizures then the withdrawal regime should not be started and that patient should continue with their prescribed medication, as per clinical practice.

#### 10.1.2.6 Administration

Phenytoin can be administered orally, intravenously or via a nasogastric tube.

## 10.1.2.7 Known drug reactions

Drug reactions are as detailed in the SmPC.

## 10.2 Concomitant Therapy

Any concomitant therapy clinically required will be permitted. Contraindications are listed in section 4.3 of the relevant SmPCs. A list of drug interactions is detailed in section 4.5 of the relevant SmPCs for both drugs. Any concomitant therapies which interact with the trial drugs will be recorded. Potential drug interactions with concomitant medications should be managed as per standard clinical practice, including therapeutic drug monitoring as appropriate. Accountability and dispensing

# 10.3 Accountability and dispensing

#### 10.3.1 Pharmacy responsibilities

IMPs will be provided directly using standard hospital stock during inpatient stay (including use of ward stock where appropriate) with no requirement for trial specific dispensing.

## 10.3.2 Drug accountability

Drug accountability is not required as the drugs will be administered in line with routine standard care practices. Compliance will be measured using inpatient records and post-discharge at 6 month follow-up.

# 11 Procedures and assessments

## 11.1 Participant identification

All patients who have been admitted to the Neurosurgical Unit (NSU) with a traumatic brain injury will be screened for eligibility for both trials based on their clinical presentation. A member of the clinical team will assess potential eligibility of these patients based on the inclusion/exclusion criteria outlined in Section 9.1 and 9.2.

